Appendix 10 - Substudy of Retrospective Acquisition of 90-day mRS

Rationale

When the 90-day mRS is not able to be obtained within the data collection window (90 days -7 days or +30 days) but the patient/family is contacted at a later date, a retrospective mRS could help to reduce missing data for the primary outcome. However, it is unclear whether collecting this retrospectively suffers from recall-bias or if it's a reasonable approach to imputing those outcomes.

Primary Aim

The goal of this substudy is to estimate the validity of acquiring the 90-day mRS at a later point of time when the patient has been lost at 90 days.

Secondary Aim

The secondary goal is to estimate the validity of acquiring the

- 1. 90 day EQ5D
- 2. quality of life
- 3. visual analog score at a later point of time when the patient has been lost at 90 days.

Approach

The 90-day mRS collected around 90 days after enrollment and either (a) retrospectively at 6 months, (b) retrospectively at 9 months, or (c) retrospectively at 12 months after hospital discharge. Two measurements per subject will be obtained and compared to each to see if the recall matches the actual mRS. To look for any decay, we will obtain the second mRS at either the 6 month, 9 month, or the 12 month visit, chosen randomly.

The same questions will be asked of the secondary outcomes.

To activate time-window specific memories, we would ask them to recollect how they were on particular specially memorable days that fell within the 2.5-3.5 month visit window, e.g. holidays (Valentine's Day, July 4, Thanksgiving, Christmas, etc) or family events (birthdays, anniversaries, etc).

Analysis

The mRS at 90 days will be compared to the retrospectively-obtained mRS using kappa statistics (if mRS is dichotomized or treated as categorical) or weighted Kappa statistics (if keep all categories and want to give some credit when the categories were close). This will be done separately for the comparisons of

- 3mo vs. 6mo
- 3mo vs. 9mo
- 3mo vs. 12mo mRS values.

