mRS, age, Black race, gender, and dichotomized time from LSN to EMS/MSU arrival (>1hr versus ≤1hr). Standardized mean differences were used to assess covariate balance before and after weighting (all standardized mean differences were < 0.1). The predicted probabilities were used to calculate stabilized inverse probability weights (IPW). The 90-day uw-mRS was further described using means and standard deviations and by fitting a univariate linear regression with outcome (90-day uw-mRS), covariate MSU group, and IPW according to the propensity score. IPW analyses of all enrolled patients was added post-hoc to assess the chances of post-enrollment selection bias and to align analysis with overall MSU vs EMS management with outcomes discharge mRS and 24hr NIHSS.

Utility weights

The sample size was originally designed using the Dawn trial utility weights that were derived based on a United Kingdom sample and using the 3-level version of EQ5D. EQ5D-5L has been in use for more than a decade. However, the corresponding population-level utility weights for 5L had not been developed for many countries, and most countries only have population-level weights for the much older EQ5D-3L. In 2019 a study was published by Pickard et al. conducted a survey to develop utilities based on a US population and using the 5-level version of EQ5D (EQ5D-5L), which is more relevant to the participants in the BEST-MSU study. Using their Probit model estimated parameters to calculate utilities, in June 2020 we fit a linear regression model with these utilities (using 90-day EQ5D-5L) as the outcome and the 90-day mRS indicator variables as the independent variables to estimate our specific utility-weighted mRS. We also applied both the Dawn and the newly derived utility weights to the B-PROUD data and observed that results were consistent in the comparison of their mobile stroke unit data and their non-mobile stroke unit groups between these two weight choices. These were presented during the June 2020 study monitoring committee and were approved to use as the primary outcome of our trial. The weights based on the June 2020 data are presented in Table.

Table. Comparison of utility weights.

mRS	Dawn weights (previous MSU weights)	ENCHANTED trial weights	New proposed MSU
0	1	0.977	1
1	0.91	0.885	0.91
2	0.76	0.748	0.72
3	0.65	0.576	0.65
4	0.33	0.194	0.18
5	0	-0.174	0.05
6	0	0	0

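### Appendix 10 raises recall bias in the 90-day mRS but plans only kappa, which measures agreement and cannot show whether recall errors run in one direction

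*Protocol*

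**What the plan says.** The rationale of Appendix 10 (protocol) is that a late, retrospective mRS might reduce missing primary outcomes, but "it is unclear whether collecting this retrospectively suffers from recall-bias or if it's a reasonable approach to imputing those outcomes". The primary aim is put as validity: "The goal of this substudy is to estimate the validity of acquiring the 90-day mRS at a later point of time". The design is paired: "Two measurements per subject will be obtained and compared to each to see if the recall matches the actual mRS". To look for decay, "we will obtain the second mRS at either the 6 month, 9 month, or the 12 month visit, chosen randomly".

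The analysis is one sentence: "The mRS at 90 days will be compared to the retrospectively-obtained mRS using kappa statistics" if the scale is dichotomized or treated as categorical, or "weighted Kappa statistics (if keep all categories and want to give some credit when the categories were close". It is run separately for 3 versus 6, 9 and 12 months. The appendix gives no signed difference, marginal-homogeneity test, split by arm, kappa weighting scheme, acceptance threshold or sample size. The secondary aims add EQ-5D, quality of life and the visual analog score, with no analysis stated for them.

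The SAP does not fill the gap. Section 5.1.6 (Missing Data) relies on multiple imputation, with results shown with and without it. Section 5.1.3 (Sensitivity Analysis of Primary Outcome) does not mention recalled values.

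**The concern.** Bias is a directional quantity: do patients remember day 90 as better or worse than it was? Kappa is built from how often, and in its weighted form how far, two ratings differ. The sign of the difference does not enter. A set of errors that cancel and a set that all point one way can therefore give nearly the same kappa, provided the amount of disagreement is similar.

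The primary outcome is a mean uw-mRS, so the mean signed error is the property that decides whether a recalled value can stand in for a missing one. Patients and families also know whether the MSU came, so a shift that differs by arm is conceivable, and the plan does not look for it.

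What is at stake is mainly the substudy's own conclusion about recall bias.

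**Working it through.** **No figure to reproduce.** Appendix 10 states no expected kappa, threshold or sample size. The check compares what kappa reports with what a signed difference reports for the same recall errors.

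**From the documents.** Utility weights for mRS 0 to 5 are 1, 0.91, 0.72, 0.65, 0.18 and 0.05 (SAP 5.1.2, new weights: "The weights based on the June 2020 data are presented in Table"). Loss to follow-up is 5% (SAP 5.1.6).

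**Assumed, not in the documents.** Survivors' mRS 0 to 5 is distributed 24/27/12/13/16/8%. Each patient has a 25% chance of a one-grade error. Errors are balanced, all toward better, or all toward worse. A patient already at the end of the scale stays there, so actual discordance is 21%, 19% and 23%.

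**Formulas.** Kappa = (po - pe)/(1 - pe), where po is observed agreement and pe is the agreement expected from the margins. The uw-mRS shift is the sum over grades of (proportion in grade) x (error rate) x (utility change for that step).

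**Kappa, unweighted:**
- balanced: (0.790 - 0.190)/(1 - 0.190) = 0.741
- all better: (0.810 - 0.196)/(1 - 0.196) = 0.764
- all worse: (0.770 - 0.184)/(1 - 0.184) = 0.718

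**Shift in uw-mRS:**
- all better: 0.25 x (0.27x0.09 + 0.12x0.19 + 0.13x0.07 + 0.16x0.47 + 0.08x0.13) = 0.25 x 0.1418 = +0.035
- all worse: 0.25 x (0.24x0.09 + 0.27x0.19 + 0.12x0.07 + 0.13x0.47 + 0.16x0.13) = 0.25 x 0.1632 = 0.041, with negative sign
- balanced: half of each, (0.0354 - 0.0408)/2 = -0.003

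| Errors | Unweighted kappa | Quadratic kappa | Kappa, 0-1 vs 2-5 | uw-mRS shift |
|---|---|---|---|---|
| Balanced | 0.741 | 0.962 | 0.903 | -0.003 |
| All better | 0.764 | 0.965 | 0.940 | +0.035 |
| All worse | 0.718 | 0.958 | 0.865 | -0.041 |

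In this example one-sided optimistic recall scores slightly higher than unbiased recall on every version of kappa. At a 15% error rate, unweighted kappa is 0.844, 0.858 and 0.830, with shifts of -0.002, +0.021 and -0.025.

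**Discordance held equal.** With 30% discordance in each case and an assumed distribution of 20/20/15/15/15/15%, unweighted kappa is 0.639, 0.637 and 0.640, and quadratic kappa is 0.950 in all three. The uw-mRS shifts are -0.002, +0.055 and -0.055. Across four assumed distributions, unweighted and weighted kappa differ by at most 0.008 between balanced and one-sided errors. Dichotomized kappa differs by up to about 0.04.

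**What a signed analysis does with the same pairs.** In simulated samples of 100 pairs with a 30% error rate, a two-sided sign test rejected 3% of the time when errors were balanced and about 100% when they were one-sided. Mean quadratic kappa was 0.958 and 0.959, with a sampling SD of about 0.009.

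**Effect on the trial.** If all 5% lost were later recalled, an arm mean would move by 0.05 x 0.035 = 0.0018 or 0.05 x 0.041 = 0.0020. If the arms erred in opposite directions, the difference would move by 0.0018 + 0.0020 = about 0.004.

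**The case against.** Much of Appendix 10 is well served by kappa. Whether recall matches, and whether agreement falls from 6 to 12 months, are agreement questions. A reader might infer that the substudy cannot answer its question at all; that goes too far, because only the directional part is left open.

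A high unweighted kappa also limits how large a shift can be. In the example, values of 0.83 to 0.86 go with one-sided shifts of 0.021 to 0.025. At a 50% error rate, one-sided shifts of 0.07 to 0.08 pull unweighted kappa down to 0.44 to 0.53. So it would be wrong to infer that recall shifted by a grade in everyone would pass unnoticed: unweighted kappa then falls to about 0.05 or below and linear kappa to 0.53 to 0.58. Only quadratic kappa stays near 0.85, and the appendix does not say which weights it will use. This stands, with one limit: a fall in kappa still does not separate bias from random error.

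A reader might also infer that a high kappa would license substituting recalled values in the primary analysis. No rule in either document says so; the appendix leaves the use of recalled values open. Finally, the missing split by arm and the missing analysis for EQ-5D and the visual analog score are gaps in the plan and not defects of kappa, which can be computed by arm and is assigned only to the mRS.

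**Conclusion.** The point holds for directional recall bias. The appendix names that question, and neither it nor the SAP contains an analysis that would reveal direction. For similar amounts of disagreement, unweighted and weighted kappa are nearly the same whether errors cancel or not, while the mean uw-mRS shift among recalled patients runs from about 0 to +0.035 or -0.041. The size rests on an assumed mRS distribution, one-grade errors and assumed error rates. The insensitivity to direction does not depend on the particular distribution chosen.

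A reader might set the shift of 0.035 beside the design difference of 0.07 and infer a threat to the trial result. The documents do not support that: 0.035 applies to a recalled patient and 0.07 to whole arms. At trial level the effect is at most about 0.002 to 0.004 with 5% lost, and that already assumes every lost patient is later reached. Protocol 7.G still quotes 10% lost; at that rate opposite errors would give 0.10 x (0.035 + 0.041) = about 0.008. This is a minor improvement to a substudy.

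**What to change.** Keep kappa or weighted kappa for agreement and decay, and state the weights. Then add to the Appendix 10 analysis:

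- the mean signed difference (recalled minus actual) in uw-mRS with a 95% CI, separately at 6, 9 and 12 months;
- a test of marginal homogeneity for the mRS (Stuart-Maxwell or Bhapkar);
- the signed difference by arm, reported descriptively because it will be imprecise;
- for EQ-5D and the visual analog score, the mean difference with limits of agreement.

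The paired data are already planned, so the cost is a few lines of text and a short analysis, with no added visit or procedure.

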1. STUDY OVERVIEW

1.1. Objective and Study Design

The primary goal of this project is to carry out a trial comparing pre-hospital diagnosis and treatment of patients with stroke symptoms using a Mobile Stroke Unit (MSU) with subsequent transfer to a Comprehensive Stroke Center (CSC) Emergency Department (ED) for further management, to standard pre-hospital triage and transport by Emergency Medical Services (EMS) to a CSC ED for evaluation and treatment (Standard Management-SM).

There are many ways that use of a MSU might prove valuable in stroke patients, but we will focus on acute ischemic stroke (AIS) and treatment with IV tissue plasminogen activator (tPA) within 4.5 hours of symptom onset since that is the most evidence based effective emergency treatment for the most prevalent stroke diagnosis. We hypothesize that the MSU pathway will produce an overall shift towards earlier evaluation and treatment, particularly into the first hour after symptom onset, leading to substantially better outcome. We will also explore the hypothesis that as a result of improved clinical outcomes resulting from earlier treatment, the costs of a MSU program will be offset by a reduction in the costs of long term stroke care and increase in quality adjusted life years, thereby supporting more widespread use of this technology. To make MSU deployment more practical, we will confirm that a Vascular Neurologist (VN) on board the MSU can be replaced by a remote VN connected to the MSU by telemedicine (TM) thereby reducing manpower requirements and costs.

The successful completion of this project will provide data on important outcomes and costs associated with the use of MSU vs SM in the United States (U.S.) that will determine the value of integrating MSUs into the pre-hospital environment that would be more generalizable throughout the country. Therefore, the proposed study is the necessary step in a process that may dramatically modify the way that acute stroke patients are managed.

This is a prospective multicenter cohort study with randomized deployment weeks and blinded assessment of both trial entry and clinical outcomes.

2. DEFINITION OF TARGET POPULATION AND STUDY SAMPLES

2.1. Target Population

No. of Clinical Sites: 6

No. of subjects:

To be assessed for eligibility	(n = 4900)
To be enrolled	(n = 1845)
To be analyzed (“tPA eligible”)	(n = 1038)

Main criteria for inclusion:

1. Criteria for MSU team to enroll a patient into the study (to be determined pre-hospital on both MSU and SM weeks)

- a. Last seen normal possibly within 4hr 30 min
- b. History and physical/neurological examination consistent with acute stroke
- c. No definite tPA exclusions per guidelines, prior to CT scan or baseline labs
- d. Informed consent obtained from patient (if competent) or legal representative. Pre-hospital management and treatment, including IV tPA, will not be delayed for consent; however, consent in both MSU and SM patients must eventually be obtained for data to be retained for analysis.

2. Criteria for **tPA-eligibility** (to be determined pre-hospital on MSU weeks, and after ED assessment on SM weeks, and confirmed by blinded adjudication)

- a. Meeting tPA inclusion and exclusion criteria per guidelines after CT scan, baseline labs, and clinical re-evaluation

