We aim to carry out a multicenter prospective cohort study with randomized MSU or SM deployment weeks and blinded assessment of both trial entry as well as clinical outcomes. Since tPA treatment will occur at different time points in the study arms, our protocol is designed to reduce the potential for bias due to lack of allocation concealment. All potential stroke patients will be identified by a 911 dispatch center adhering to current standard of care protocols and subsequently screened for trial inclusion (confirmed neurological deficits with onset well within the IV-tPA treatment window and typical stroke mimics such as hypoglycemia excluded) at the same pre-hospital time by the same investigators on both MSU and SM weeks to ensure that comparisons are made between similar patients. Anyone transported on the MSU (or SM patients who are deemed eligible for MSU transport) will be considered as enrolled into the study and eventually consented for participation. Therefore, comparable patients in the SM group will also be enrolled and consented. For all patients enrolled, criteria for study enrollment and tPA treatment will be subsequently reviewed by a vascular neurologist blinded to MSU vs SM assignment. For comparing outcomes between MSU and SM, we will only include patients meeting criteria for tPA treatment, whether or not actually treated, based on a blinded review of prehospital information. We will report baseline comparability of clusters (patient co-morbidities, age, stroke severity), plan an intention-to-treat analysis, and will implement an aggressive protocol to reduce lost to follow-up and thus differential missing data. Finally, all 3 month mRS measurements will utilize a standardized questionnaire (Rankin Focused Assessment) which will be obtained from the patient by an investigator blinded to treatment allocation.

5.A. Inclusion Criteria

There will be three decision points for inclusion of patients into either the MSU or SM arms (see flow chart, Appendix 1): 1. Whether to call the MSU team at the time of the 911 call or EMT evaluation; 2. Whether the patient might be a tPA candidate when evaluated by the MSU team pre-hospital; 3. Whether the patient meets criteria for IV tPA treatment.

1. Criteria to alert MSU Team (by either a, b, c, or d, and meeting all criteria i-iv):

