The MSU is not dispatched, but the MSU RN or VN is 5.C.4. Standard management: dispatched by car to the scene or meets the patient and EMS squad at the destination ED. The destination CSC is determined by EMS (these are the same complement of hospitals served by the MSU) and the hospital stroke team is pre-notified by EMS. Once on scene or at the ED, the patient's history, time last seen normal, vital signs, finger stick glucose, and physical examination are obtained from the EMS paramedics by the MSU VN or RN who then carry out their own NIHSS without delaying the EMS evaluation, transport or ED intake process, If the patient meets all inclusion criteria except lab and CT (which have not yet been done), the patient is then enrolled into the study for purposes of answering the Specific Aims, and assigned to the SM arm. If the patient does not have signs and symptoms of a stroke, is clearly outside the 4.5 hour time window, has other definite tPA exclusions, or is clinically unstable (such as requiring pressor or ventilator support), they are not enrolled and are managed per EMS and ED routine. These patients are considered "screen failures" and a one page CRF completed including diagnosis and reason for exclusion. Following the decision to enroll the patient, the MSU VN or RN then decide if the patient meets criteria for tPA. If the patient meets all inclusion and exclusion criteria for thrombolysis according to published guidelines during the pre-hospital evaluation by EMS and the MSU team, and if the baseline labs and CT scan obtained once the patient reaches the ED do not exclude the patient, then the patient is considered a "SM tPA-eligible patient", whether or not they eventually receive tPA in the ED (for instance, the 4.5 hour time window might be exceeded, or the patient's deficit might have resolved, by the time the patient is fully evaluated in the ED).

The hospital based stroke team manages the patient as per stroke center routine and the same standard of care analyses carried out as with the MSU treatment. IV tPA is given as per the hospital based stroke team. If the patient does receive tPA in the ED, the "therapy decision time", and "tPA needle time" are recorded. For all SM enrolled patients, whether or not they actually receive tPA, the RN or VN obtain consent, and visit the patient on days 0-3 at the hospital and day 90 in clinic or at home, and record study related data on the CRF.

TM is not carried out on SM weeks.

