2.2.3. Safety Outcomes

- The incidence of symptomatic intracranial hemorrhage (sICH) in enrolled tPA treated patients on MSU weeks compared to SM weeks (Symptomatic intracranial hemorrhage defined as any intracranial blood accumulation associated with a clinical deterioration of ≥ 4 points of the NIHSS for which the hemorrhage has been identified as the dominating cause of the neurologic deterioration) N.B. Patients will include all patients treated with tPA, whether or not they meet all inclusion and exclusion criteria.
- Mortality. N.B. All enrolled patients signing informed consent will be included in this endpoint and followed until 1 year.
- The incidence of stroke mimics and transient ischemic attacks (TIAs) in tPA-treated patients, and also in tPA-eligible patients, on MSU weeks compared to SM weeks. N.B. SM patients deemed eligible for tPA on their pre-hospital assessment who then completely recover by the time of arrival in the ED will equal the excess incidence of TIAs treated on the MSU pathway.

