3. GENERAL STATISTICAL CONSIDERATIONS

3.1. Randomization and Analytic Cohorts (The process is described in detail in the protocol)

Weeks when the MSU is available or not are randomly selected. Stroke events are orthogonal to whether the MSU was being deployed or not that week and thus participants will be randomly

entered into either the MSU or SM groups depending on when their stroke occurs.

The primary analytic cohort is based on a modified intention-to-treat (ITT) analysis where the subject will be assigned to the group that they were enrolled in (e.g. if a patient was enrolled using SM, they would be assigned to the SM group) and adjudicated (by the blinded adjudicator) to be tPA eligible. The usual ITT includes every subject who is randomized according to randomized treatment assignment. In this study, all patients within each group who are adjudicated as tPA eligible by an adjudicator blinded to group assignment are included. The randomized assignment is not conducted for each patient, rather we generally alternated weeks to be either MSU or SM weeks, which is independent of when a subject randomly has a stroke and calls 911. Therefore, this may be considered a cluster-randomized trial where the cluster is the days when the MSU is available and the other cluster is when MSU is not available. There is not anything clinically important to set the cluster of when the MSU was available or not as a week (e.g., an alternative design could set one week as having MWF as MSU days and TTH as SM days and the next week as the opposite), but this made it convenient to set work schedules and to have a similar amount of time dedicated to recruitment of MSU and SM subjects and there is not a scientific nor statistical rationale suggesting that the clusters would be related to the patient's outcomes and intervention effect. Patients are, in a sense, "randomly" allocated into the clusters based entirely on when they happen to have their stroke in relation to the prospectively determined cluster allotment of whether the MSU is available or not. Furthermore, in order to optimize the utilization of the MSU, some cities have 2 sites enrolling patients at the same time, with one site running the MSU and other enrolling SM patients and then they switch the next week.

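### The tPA-eligibility rule that forms the primary cohort is unreconciled: read literally, SAP 2.1 would exclude early recoverers more often on SM than on MSU weeks, while Protocol 5.C.4 keeps them

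*SAP*

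**What the plan says.** **Who is analysed.** SAP 3.1 defines the primary cohort as a modified intention-to-treat set in which "all patients within each group who are adjudicated as tPA eligible by an adjudicator blinded to group assignment are included". Whatever defines tPA eligibility therefore defines the primary comparison.

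**Rule A.** SAP 2.1 says eligibility is "to be determined pre-hospital on MSU weeks, and after ED assessment on SM weeks, and confirmed by blinded adjudication". The criterion is "Meeting tPA inclusion and exclusion criteria per guidelines after CT scan, baseline labs, and clinical re-evaluation". The protocol synopsis and Protocol 5.A (criterion 3) say the same.

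**Rule B.** Protocol 5.C.4 defines the SM tPA-eligible patient as one who meets the thrombolysis criteria "during the pre-hospital evaluation by EMS and the MSU team, and if the baseline labs and CT scan obtained once the patient reaches". As that sentence continues, ED results must not rule the patient out. Such a patient stays eligible even if untreated, and one of the examples given is that "the patient's deficit might have resolved, by the time the patient is fully evaluated in the ED".

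**What the adjudicator sees.** Protocol 5 (Study Design) restricts outcome comparisons to patients who meet tPA criteria "based on a blinded review of prehospital information". Protocol 6.A.1 and SAP 2.2.1 refer instead to a blinded review of the chart. Protocol 5.D and SAP 3.2 say the adjudication form carries no time data or other unblinding information. Neither says whether an SM patient's form shows the pre-hospital or the ED examination.

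**Early recoverers are expected.** SAP 2.2.3 refers to SM patients judged eligible pre-hospital "who then completely recover by the time of arrival in the ED will equal the excess incidence of TIAs", meaning those given tPA in the MSU arm.

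**The concern.** A patient with a transient deficit is likely to have a good 90-day score. If that patient has a stroke on an MSU week, the eligibility decision is made on board, soon after first contact. On an SM week, Rule A makes it after transport and ED work-up, which leaves more time to recover and fail the re-evaluation. Rule B would keep the same SM patient.

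Under Rule A, good-outcome patients would leave the comparator more often than the MSU arm. The SM mean would fall and MSU would look better for a reason unrelated to treatment.

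Blinding the adjudicator does not prevent this. If the form shows the ED examination for SM patients, a reviewer who applies Rule A correctly and blind would still exclude the recovered ones. The selection would lie in what the form contains.

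**Working it through.** **1. The plan's own figure.** SAP 4.1 gives a difference of 0.07, SD 0.385, MSU:SM 1.5, 5% lost to follow-up and N = 1038. It states 80% power and 0.05 error for the earlier N = 693; I assume both carry over, two-sided.
- SM n = (1 + 1/1.5) × [0.385 × (1.960 + 0.842) / 0.07]² ≈ 396. MSU n = 1.5 × 396 = 594. Total 990.
- 990 / 0.95 = 1043 and 990 × 1.05 = 1040. Without rounding, 989.3 × 1.05 = 1038.8.
- With 1038 × 0.95 = 986 evaluable, power is 79.9%.

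The sample size reproduces. The eligibility question does not enter it; 0.07 serves below only as a yardstick.

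**2. The two rules side by side, for an SM patient.**

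| | SAP 2.1, synopsis, Protocol 5.A (criterion 3) | Protocol 5.C.4 and 5 |
|---|---|---|
| Clinical status judged | After ED assessment, with re-evaluation | At the pre-hospital evaluation |
| What the ED can exclude on | CT, laboratory results, re-evaluation | CT and laboratory results |
| Deficit resolved before full ED evaluation | Not addressed; fails on a literal reading | Stays eligible |

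**3. Size of the shift if recoverers are removed.** Let f be the fraction of SM candidates removed for recovery, u their mean uw-mRS and m the SM mean before removal. Removing them lowers the SM mean by f(u − m)/(1 − f). The value of f is not in the documents; u and m are assumed.

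With m = 0.60 and u = 0.95:
- f = 5%: 0.05 × 0.35 / 0.95 = 0.018, which is 26% of 0.07.
- f = 10%: 0.10 × 0.35 / 0.90 = 0.039, which is 56% of 0.07.

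Using values tied to the documents, take u = 0.91 to 1.0 (weights for mRS 1 and 0, SAP 5.1.2) and m = 0.50 to 0.59 (NINDS placebo and tPA means, Protocol 6.A.1):
- f = 2%: 0.007 to 0.010 (9–15% of 0.07).
- f = 5%: 0.017 to 0.026 (24–38%).
- f = 10%: 0.036 to 0.056 (51–79%).

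**4. Effect on the test.** SE = 0.385 × √(1/394.4 + 1/591.7) = 0.0250. For a shift b, the two-sided type I error is 1 − Φ(1.96 − b/SE) + Φ(−1.96 − b/SE). The f = 5% range gives about 10–18%. This is for the unadjusted comparison of means.

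**5. Removal in both arms.** The figures above assume no removal on MSU weeks. With m = 0.60 and u = 0.95 in both arms, 8% removed on SM lowers its mean by 0.08 × 0.35 / 0.92 = 0.030, and 5% removed on MSU lowers its mean by 0.018. The net shift is 0.012, or 17% of 0.07.

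**6. Under Rule B** no scene-enrolled SM patient is removed for recovery, so this shift is zero for them.

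**The case against.** The best defence is that Rule A is only a one-line list of main criteria. On SM weeks CT and laboratory results exist only in the ED, so eligibility cannot be settled earlier, and the wording may mean no more than that. SAP 2.1 nowhere says a recovered SM patient is dropped. SAP 2.2.3 also speaks of SM patients eligible on their pre-hospital assessment, which fits 5.C.4, and plans TIA and mimic incidence among tPA-eligible patients by arm, which would help reveal a shortage on SM weeks. This reading is plausible. It does not explain the re-evaluation item or settle which examination the adjudicator sees.

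Three stronger readings are tempting and are not supported:

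- **That only SM loses recoverers.** Protocol 5.C.3 has the on-board neurologist complete the examination, including NIHSS, after CT and before deciding, and tPA is deferred if the patient no longer qualifies. The arms differ in when recovery can exclude a patient, not in whether it can.
- **That the SAP overrides 5.C.4.** No passage ranks the documents this way, and the heading of SAP 3.1 refers to the protocol for process detail.
- **That the run-in gives the fraction.** Protocol 4.C reports 2 TIAs among 25 enrolled patients, but these were MSU-week patients transported untreated. They show that TIAs occur and say nothing about an SM excess.

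The primary model in SAP 5.1.2 adjusts for baseline NIHSS, so the raw-mean figures need not carry over to it unchanged.

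The existing analyses do not close the gap. The all-enrolled cohort is post hoc (SAP 3.1), and SAP 5.1.2 ties its weighted analysis to discharge mRS and 24-hour NIHSS. Neither would detect patients never enrolled: 5.C.4 lets the SM team first meet a patient at the ED, where someone without stroke signs is not enrolled. Protocol 5 and 5.L say screening happens at the same pre-hospital time in both arms.

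**Conclusion.** The concern holds as an unreconciled definition of the primary cohort. Two rules stand in the documents, they give different answers for an SM patient who recovers before full ED evaluation, and nothing says which one the adjudication form implements.

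Taken literally, SAP 2.1 would remove early recoverers more often on SM than on MSU weeks and so favour MSU. A net excess removal of 5% of SM candidates, with assumed means of 0.60 and 0.95, would shift the contrast by about 0.018, or 26% of the design difference. That is an illustration: the fraction is unknown and removal on MSU weeks would reduce the shift. If 5.C.4 was followed, the shift is zero for patients enrolled at the scene; SM patients first assessed at the ED remain a smaller open question. A reader should not infer that the trial did lose SM recoverers, because the documents do not show which rule was applied.

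**What to change.** Confine the change to the adjudicated analysis cohort. Protocol 5.A (criterion 3) is also the point at which treatment is decided, and that should be left alone.

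1. Carry the 5.C.4 definition into SAP 2.1 as the definition of the analysis cohort, with a cross-reference from the synopsis and 5.A.
2. State that in both arms the blinded adjudicator judges the pre-hospital examination together with CT and laboratory results, and that resolution before ED evaluation does not remove a patient from the primary cohort.
3. Make the adjudication form show that examination in both arms.
4. Report by arm how many enrolled patients were adjudicated ineligible because of recovery, and how many SM patients were first assessed at the ED.
5. Add a sensitivity analysis excluding TIAs and early recoverers from both arms. Dropping SM recoverers alone would recreate the bias. It should be supportive only, because recovery on MSU weeks may follow tPA, so the exclusion could also remove treatment benefit.

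The cost is wording changes and limited re-adjudication from existing records. The sample size does not change.
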